## 3.0 Patient Eligibility

- 3.1 Inclusion criteria
  - 3.11 Age  $\geq$ 18 years
  - 3.12 Advanced, incurable cancer
  - 3.13 7th or later cycle of intravenous carboplatin or oxaliplatin infusion planned or 4 months after the first cycle of agent (whichever is of longer duration)  $\leq$ 30 days after registration
  - 3.14 Anticipated 2 or more subsequent chemotherapy infusions of either carboplatin or oxaliplatin at the time of study registration.  
NOTE: The dose of carboplatin or oxaliplatin, choice of other chemotherapy, and other ancillary treatment, such as antiemetics, will be left to the discretion of the treating healthcare provider.
  - 3.15 Willing to provide mandatory blood and urine specimens for correlative research.  
Note: Can be waived with permission of Study Chair (documentation such as an email must be provided).
  - 3.16 The following laboratory values obtained  $\leq$ 30 days prior to registration:
    - Serum creatinine  $\leq$ 1.5 times the institutional upper limit of normal (ULN)  
Note: Can be waived with permission of Study Chair (documentation such as an email must be provided).
    - Aspartate aminotransferase (AST) or Alanine aminotransferase (ALT)  $<3$ x the upper limit of normal.
    - Triglycerides  $<500$  mg/dL
    - Alkaline phosphatase  $\leq$ 3x the institutional upper limit of normal.
- 3.2 Exclusion Criteria
  - 3.21 Concurrent liposomal doxorubicin or any other liposomal agent.
  - 3.22 Prior carboplatin or oxaliplatin hypersensitivity reaction.
  - 3.23 Taking aspirin, nonsteroidal anti-inflammatory agents, or zileuton  $\leq$ 7 days prior to registration.  
Note: Can be waived with permission of Study Chair (documentation such as an email must be provided).
  - 3.24 Allergy to egg or egg byproducts.

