### 6.3 Verification

Prior to accepting the registration, registration application will verify the following:

- Patient eligibility
- Existence of a signed consent form
- Existence of a signed authorization for use and disclosure of protected health information

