### 6.6 Randomization and Blinding Procedures

6.61 The factors defined in Section 5.0 will be used as stratification factors.

6.62 After the patient has been registered into the study, the values of the stratification factors will be recorded, and the patient will be assigned to one of the following treatment groups using the Pocock and Simon dynamic allocation procedure which balances the marginal distributions of the stratification factors between the treatment groups.

- Chemotherapy agent: carboplatin versus oxaliplatin

6.63 The Registration Office will notify the Pharmacy of the assigned arm.

6.64 Blinding will be ensured by means of masking the infusion bag and the associated tubing. Only the pharmacy staff will know if a specific patient is receiving lipids versus saline.

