## 7.0 Protocol Treatment

### 7.1 Treatment Schedule

Agent/Placebo	Dose	Route	Days 	Retreatment
Intralipid®	100 mL	IV	immediately prior to each dose of either carboplatin or oxaliplatin until the patient demonstrates a healthcare provider-witnessed hypersensitivity reaction	continue with each dose of chemotherapy
Placebo	100 mL	IV	immediately prior to each dose of either carboplatin or oxaliplatin until the patient demonstrates a healthcare provider-witnessed hypersensitivity reaction	continue with each dose of chemotherapy

- 1 Maximum Cycle Length will be 28 days. Cycle length will vary depending on the cycle of the chemotherapy regimen.
2. For all other chemotherapy agents, administer premeds, chemotherapy, lipid infusion, and then Carboplatin or Oxaliplatin.
3. Initiate infusions at 30 mL/hour (0.5 mL/minute) for 15 minutes; if no untoward effects occur, the infusion rate may be increased to 60 mL/hour (1 mL/minute) for 92.5 minutes. Subsequent infusions may be administered over 1 hour.

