#### 15.12 Formulation:

The lipid emulsion used in this study will consist of 100 mL of Intralipid® 20%, which contains 20% soybean oil, 1.2% egg yolk phospholipids, 2.25% glycerin, and water for injection. The major fatty acid components include linoleic acid (44-62%), oleic (19-30%), palmitic (7-14%), linolenic (4-11%), and stearic (1.405.5%). Intralipid 20% is available in 100 mL, 250 mL, and 500 mL fill sizes. The Intralipid 20% utilized in this study will be supplied in a 100 mL bags.

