**Frequency not defined:**

Gastrointestinal: Gallbladder disease

Genitourinary: Urinary tract infection

Hepatic: Hepatic abnormality

Infection: Septicemia

Miscellaneous: Fever

<1% (Limited to important or life-threatening): Decreased INR, diarrhea, hypersensitivity reaction (including rash and dyspnea)

Consult the package insert for the most current and complete information.

**15.18 Drug procurement:** This product is manufactured by Fresenius Kabi, Uppsala, Sweden for Baxter Healthcare Corporation, Deerfield, IL.

Drug will be purchased through our usual pharmacy purchasing channels and received at the following shipping addresses:

Mayo Clinic Rochester  
Attn: Cancer Center Research Pharmacist  

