### 16.2 Study Design

This is a prospective randomized study to explore whether the infusion of a lipid emulsion (versus placebo) prior to carboplatin or oxaliplatin in high risk patients leads to a decrease in incidence of hypersensitivity reactions. Patients will be randomized in a 1:1 ratio to receive a lipid emulsion versus placebo.

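### Section 3.24 excludes egg allergy but not allergy to soybean or any other emulsion component, so a patient with known soy allergy is eligible and could be randomized to the emulsion

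*Combined protocol and SAP*

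**What the plan says.** Section 3.2 has four exclusions: concurrent liposomal agents (3.21), a prior reaction to carboplatin or oxaliplatin (3.22), recent aspirin, NSAID or zileuton use (3.23), and "Allergy to egg or egg byproducts" (3.24). Unlike 3.23, 3.24 has no waiver note. The inclusion criteria in 3.1 do not mention allergy.

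Section 15.12 describes the study product as Intralipid 20%, "which contains 20% soybean oil, 1.2% egg yolk phospholipids, 2.25% glycerin, and water for injection". Section 1.4 also singles out soy-based emulsions in its rationale. Among important or life-threatening events below 1%, Section 15.17 lists "hypersensitivity reaction (including rash and dyspnea"), and then directs the reader: "Consult the package insert for the most current and complete information".

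On the route to treatment, Section 6.3 begins "Prior to accepting the registration, registration application will verify the following", and the items that follow are eligibility, a signed consent form and a signed authorization. Section 16.2 states: "Patients will be randomized in a 1:1 ratio to receive a lipid emulsion versus placebo". Under 6.64, "Only the pharmacy staff will know if a specific patient is receiving lipids versus saline". Section 7.1 gives the infusion "immediately prior to each dose of either carboplatin or oxaliplatin until the patient demonstrates a healthcare provider-witnessed hypersensitivity reaction".

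**The concern.** The protocol screens for allergy to one ingredient of the infused product and is silent on the others, including the main one. It gives no reason for treating egg and soybean differently. A site that follows Section 3.0 exactly would register a patient with a recorded soy allergy, and the registration check would confirm that patient as eligible.

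What is at stake is patient safety. These patients have advanced, incurable cancer, and the emulsion's preventive benefit is the hypothesis under test. An avoidable reaction to the study product would be hard to justify if one line of eligibility text could have prevented it. The trial's statistical conclusions are not materially affected.

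**Working it through.** The plan states no figure on this point, so there is none to reproduce. The check is a reading of the text, followed by a bounded illustration.

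**1. Is soy covered anywhere in eligibility?** No. None of the criteria in 3.1 or 3.2 names soy, soybean, or hypersensitivity to the emulsion or its components.

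**2. Is soybean oil the main non-water ingredient?** Yes. Section 15.12 lists soybean oil at 20%, glycerin at 2.25% and egg yolk phospholipids at 1.2%; the rest is water. Only this ordering is used here.

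**3. What happens to a patient with known soy allergy who meets the other criteria?** The patient passes verification (6.3), is randomized 1:1 (16.2) and so has a chance of about 1/2 of receiving the emulsion before each platinum dose (7.1). Bedside staff do not know the assignment (6.64).

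**4. Which other provisions could intervene?**

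- Before exposure: the baseline history and exam (4.1); baseline grading of allergic reaction (10.61); the requirement that treatment start under clinical supervision (6.4); removal before treatment (13.3); investigator discretion (13.4); and the package insert, which 15.17 points to and 10.2 uses as one source for deciding which events are expected. Any of these might catch the patient. None requires anyone to ask about soy or to withhold the emulsion.
- After exposure: the slow start of the first infusion and stopping at a witnessed reaction (7.1); removal for an immune reaction (13.4); and the rules in 16.82 for suspending accrual, which include Grade 3 or higher events at least possibly attributable to lipids on the lipid arm. These limit harm but do not prevent the first exposure.

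**5. How many patients might be involved?** The documents give no prevalence of soy allergy. Assume 0.5% to 2%, with 20 patients per arm (16.4).

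- Expected soy-allergic patients among all 40: 40 × 0.005 = 0.2 to 40 × 0.02 = 0.8.
- Expected among the 20 on lipids: 20 × 0.005 = 0.1 to 20 × 0.02 = 0.4.
- Chance of at least one on lipids: 1 − 0.995^20 = 0.095 to 1 − 0.98^20 = 0.332, or about 10% to 33%.

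**6. Can this be carried through to reactions?** Not usefully. The documents give no probability that a soy-allergic patient reacts to this product. If 5% to 50% is assumed as well, the chance of at least one reaction runs from 1 − (1 − 0.005 × 0.05)^20 = 0.005 to 1 − (1 − 0.02 × 0.5)^20 = 0.182. That is roughly a 36-fold span from two unsupported assumptions, and it supposes that no clinician acts on a known allergy. It shows that the risk cannot be sized; it is not an estimate. The below-1% line in 15.17 is not attributed to soy and cannot stand in for the missing rate.

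**The case against.** The strongest reply is that the harm premise is not in the documents. They do not say that soy allergy is a contraindication, that soybean oil carries soy allergen, or that any listed reaction is due to soy. The package insert, which could settle this, is not available here. This stands. It limits the claim to an unexcluded ingredient allergy whose hazard is inferred, and it is why the insert must be read before the wording is changed.

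A second reply is that a clinician who knows of a soy allergy would probably not start the infusion, and that the protocol provides several openings to act (4.1, 6.4, 10.61, 13.3, 13.4). This also stands in part and lowers the probability. However, the protocol did not leave egg allergy to judgement, and nothing in it explains why soy should be treated differently. Consent pages were removed from the copy reviewed, so a warning about soy may appear there; it would not be an eligibility rule.

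A reader might go further than the documents allow in three ways:

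- *That soybean oil's larger share, or the amount accumulated over many cycles, makes it the greater allergic hazard.* The documents give no allergen content for either ingredient, so quantity does not measure risk. A patient who reacts stops under 7.1 and 13.4, so large cumulative amounts would be reached only by patients who tolerate the product.
- *That a reacting patient could be kept on treatment because Section 8.0 addresses unexpected toxicity while hypersensitivity is listed.* Section 13.4 takes a patient off study for an immune reaction whether or not it was expected, so the wording of 8.0 changes nothing.
- *That soy reactions would distort the primary endpoint.* The lipid infusion comes before the platinum (7.1), and 16.31 counts reactions from carboplatin or oxaliplatin. With fewer than one soy-allergic patient expected on lipids at the assumed prevalence, any effect is negligible.

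**Conclusion.** The gap holds as a matter of text: a patient with known soy allergy who meets the other criteria is eligible, and no written rule prevents that patient from being given the emulsion. It is more than missing detail, because applying the eligibility section correctly produces this outcome.

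Its weight is modest. Whether soy allergy is a hazard with this product is an inference from 15.12 that the package insert must confirm. The probability is low, and the risk cannot be sized from the documents. The figures for patients affected rest entirely on the assumed prevalence. The documents do not support reading this as a known contraindication that the sponsor overlooked, or as a threat to the trial's result. It is a minor safety improvement worth making because it costs so little.

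**What to change.** Check the package insert, then reword 3.24 along these lines: *Known allergy or hypersensitivity to egg, soybean, or any other component of the lipid emulsion (see 15.12).*

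The change needs no new test, since allergy history can be taken at the baseline history and exam already scheduled in 4.1. The existing eligibility check in 6.3 would then cover it. The sample size is unchanged. The downside is that a few soy-allergic candidates would be excluded, fewer than one of 40 on the prevalence range assumed above.

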#### 4.0 Test Schedule

##### 4.1 Study Calendar

Tests and procedures	≤30 days prior to registration	With the first on-study infusion of carboplatin or oxaliplatin	Immediately before each infusion of carboplatin or oxaliplatin	End of each cycle of carboplatin or oxaliplatin
History and exam including weight	X			X 
Serum creatinine	X			
AST or ALT	X*			
Triglycerides	X			
Alkaline phosphatase	X*			
Lipid/placebo infusion			X	
AE Assessment	X			X
Blood and urine collection for research purposes R		X		

\*Should be retested every 3 months or per the discretion of the treating oncologist.

Maximum Cycle Length = 28 days (will vary by regimen)

Footnotes:

1. Weight only

R Research funded

##### 4.2 Event Monitoring/Survival Follow-up

Once patient is no longer on treatment for this study, no further follow-up is required.

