### 10.4 Expedited Reporting Requirements for Commercial or Commercial Imaging Agents (Non-IND/IDE) Agent(s) ONLY:

#### 10.4.1 Expedited Reporting Requirements for Adverse Events that Occur in a Non-IND/IDE trial within 30 Days of the Last Administration of a Commercial Agent

##### **FDA REPORTING REQUIREMENTS FOR SERIOUS ADVERSE EVENTS (21 CFR Part 312)**

**NOTE:** Investigators **MUST** immediately report to the sponsor **ANY** Serious Adverse Events, whether or not they are considered related to the investigational agent(s)/intervention (21 CFR 312.64)

An adverse event is considered serious if it results in **ANY** of the following outcomes:

- 1) Death
- 2) A life-threatening adverse event
- 3) An adverse event that results in inpatient hospitalization or prolongation of existing hospitalization for ≥ 24 hours
- 4) A persistent or significant incapacity or substantial disruption of the ability to conduct normal life functions
- 5) A congenital anomaly/birth defect.
- 6) Important Medical Events (IME) that may not result in death, be life threatening, or require hospitalization may be considered serious when, based upon medical judgment, they may jeopardize the patient or subject and may require medical or surgical intervention to prevent one of the outcomes listed in this definition. (FDA, 21 CFR 312.32; ICH E2A and ICH E6).

**ALL SERIOUS** adverse events that meet the above criteria **MUST** be immediately reported to the sponsor within the timeframes detailed in the table below.

Hospitalization	Grade 1 Timeframes	Grade 2 Timeframes	Grade 3 Timeframes	Grade 4 & 5 Timeframes
Resulting in Hospitalization ≥24 hrs		7 Calendar Days		24-Hour 3 Calendar Days

Not resulting in Hospitalization ≥24 hrs	Not required	7 Calendar Days	
Expedited AE reporting timelines are defined as: 
 
○ "24-Hour; 3 Calendar Days" - The AE must initially be reported within 24 hours of learning of the AE, followed by a complete expedited report within 3 calendar days of the initial 24-hour report.
 
○ "7 Calendar Days" - A complete expedited report on the AE must be submitted within 7 calendar days of learning of the AE.
 
			

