 Serious adverse events that occur more than 30 days after the last administration of investigational agent/intervention and have an attribution of possible, probable, or definite require reporting as follows: Expedited 24-hour notification followed by complete report within 3 calendar days for: 
 
• All Grade 4, and Grade 5 AEs
 
 Expedited 7 calendar day reports for: 
 
• Grade 2 adverse events resulting in hospitalization or prolongation of hospitalization
 
• Grade 3 adverse events
 
  For studies using PET or SPECT IND agents, the AE reporting period is limited to 10 radioactive half-lives, rounded UP to the nearest whole day, after the agent/intervention was last administered. Footnote "1" above applies after this reporting period.			
Effective Date: May 5, 2011			

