#### 10.52 Death

**Note: A death on study requires both routine and expedited reporting regardless of causality, unless as noted below. Attribution to treatment or other cause must be provided.**

Any death occurring within 30 days of the last dose, regardless of attribution to an agent/intervention under an IND/IDE requires expedited reporting within 24-hours.

Any death occurring greater than 30 days with an attribution of possible, probable, or definite to an agent/intervention under an IND/IDE requires expedited reporting within 24-hours.

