10.62 All other AEs

Submit via appropriate MCCC Case Report Forms (i.e., paper or electronic, as applicable) the following AEs experienced by a patient and not specified in Section 10.6:

10.621 Grade 1 and 2 AEs deemed *possibly, probably, or definitely* related to the study treatment or procedure.

10.622 Grade 3 and 4 AEs regardless of attribution to the study treatment or procedure.

10.623 Grade 5 AEs (Deaths)

10.6231 Any death within 30 days of the patient's last study treatment or procedure regardless of attribution to the study treatment or procedure.

10.6232 Any death more than 30 days after the patient's last study treatment or procedure that is felt to be at least possibly treatment related must also be submitted as a Grade 5 AE, with a CTCAE type and attribution assigned.

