**13.4 Off study**

Patients will go off study for the following reasons:

- Investigator discretion
- Treatment related adverse event (immune reaction or unexpected CTCAE  $\geq$ Grade 3 event)
- Switching to different chemotherapy
- Refusal of further treatment on this study
- Death

Patients will go off study and no further follow-up is required.

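### No follow-up is required once study treatment stops, yet Section 10 needs serious events and deaths to day 30 and related ones later, so complete capture is not assured

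*Combined protocol and SAP*

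**What the plan says.** Section 4.2, on event monitoring and survival follow-up, reads: "Once patient is no longer on treatment for this study, no further follow-up is required". Section 13.4 lists the off-study reasons (investigator discretion, treatment-related adverse event, change of chemotherapy, refusal, death) and closes: "Patients will go off study and no further follow-up is required".

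Section 10 asks for information from after that point:

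- 10.4.1 sets expedited reporting of serious adverse events "within 30 Days of the Last Administration of a Commercial Agent".
- Footnote 1 to that table adds "Serious adverse events that occur more than 30 days after the last administration of investigational agent/intervention" if their attribution is possible, probable or definite. It gives no end date.
- 10.6231 requires routine reporting of "Any death within 30 days of the patient's last study treatment or procedure", whatever the attribution. 10.6232 adds later deaths judged at least possibly related.

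The calendar in 4.1 places adverse-event assessments before registration and at the end of each cycle, with a maximum cycle length of 28 days. It has no column after treatment. Sections 10.7 and 18.2 refer the reader to a Forms Packet and a Data Submission Schedule, which are not part of the document. Section 16.82 suspends accrual if any Grade 5 event related to the lipid or placebo infusion is observed.

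**The concern.** A duty to report an event does not tell the study team that the event has happened. Sections 4.2 and 13.4 release the site from contact at the point where the 30-day window in Section 10 begins to run, and no visible section says who looks for events in that window, or how.

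The timing is awkward. Under 7.1 the infusions continue until a witnessed reaction. Under 8.0 and 13.4 an immune reaction, or unexpected toxicity of Grade 3 or higher, takes the patient off study. For these patients the obligation to follow lapses just after the event whose course and outcome matter most for safety. All patients have advanced, incurable cancer (3.12), so deaths within 30 days are plausible. Section 6.4 requires only that treatment begin at the study site, so a later event may occur elsewhere.

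The safety summary is at stake, and with it two monitoring provisions: the Grade 5 trigger in 16.82, and the review in 16.84 of Grade 4 and 5 events thought unrelated or unlikely to be related. Both presuppose that the events are known.

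**Working it through.** The plan gives no figure for post-treatment observation, so there is none to reproduce. The check has two parts.

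**1. The sections side by side**

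| What Section 10 needs | Period | Planned means of learning of it |
|---|---|---|
| Serious adverse events (10.4.1) | to day 30 after last administration | end-of-cycle assessment, if it takes place; nothing after it |
| Related serious adverse events (10.4.1, footnote 1) | after day 30, no end date | none stated |
| All deaths (10.6231) | to day 30 after last study treatment or procedure | as for the first row |
| Deaths at least possibly related (10.6232) | after day 30 | none stated |

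Section 10.7 covers how late events are submitted, not how they are found. Section 18.2 points back to Section 4.0 and to the external schedule.

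**2. How much of the 30-day window has no planned assessment**

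Inputs:

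- window of 30 days (10.4.1, 10.6231)
- maximum cycle length of 28 days (4.1)
- 40 patients (16.4)
- expected treatment time of 4 months per patient (16.5)

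Assumptions: the last infusion is on day 1 of its cycle, and a month is 30 days. The 21- and 14-day cycle lengths are also assumed, because the documents give only the maximum.

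Expected treatment time: 40 × 4 = 160 patient-months.

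If the end-of-cycle assessment takes place after the last infusion, the uncovered days per patient are 30 − C, where C is the cycle length. Over the trial this is 40 × (30 − C) / 30 patient-months.

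| Case | Uncovered days per patient | Patient-months over 40 patients | Share of 160 |
|---|---|---|---|
| C = 28 (stated maximum) | 30 − 28 = 2 | 40 × 2 / 30 = 2.7 | 1.7% |
| C = 21 (assumed) | 30 − 21 = 9 | 40 × 9 / 30 = 12 | 7.5% |
| C = 14 (assumed) | 30 − 14 = 16 | 40 × 16 / 30 = 21.3 | 13.3% |
| Off study at the last infusion, no later assessment | 30 | 40 × 30 / 30 = 40 | 25% |

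The last row is the limit if all 40 patients left that way. For an individual who leaves at a reaction, the 30 days are what 4.2 and 13.4 allow. The trial's figure lies between the rows and depends on how many patients leave at an infusion, which the plan does not give. Beyond day 30 nothing is planned in any case.

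**The case against.** The best defence is that the text does not cancel anything. It says follow-up is not mandatory, under a heading about event monitoring and survival, which can fairly be read as meaning that there is no survival phase. The Section 10 duties still bind, 10.7 foresees late events, and the external packet or schedule may say how they are found. This stands against one tempting reading: that the plan ends all follow-up and its safety data will be incomplete. The documents do not show that. They show that completeness is not assured by anything in them.

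A second point is that the end-of-cycle assessment can cover up to 28 of the 30 days. A reader might infer that a quarter as much time again goes unobserved. That 25% needs every patient to leave at the last infusion with no later assessment, so it is an extreme upper bound.

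Third, 10.52 looks like the plainest statement of the death requirement, but in full it reads: "Any death occurring within 30 days of the last dose, regardless of attribution to an agent/intervention under an IND/IDE requires expedited reporting within 24-hours". Section 10.4 is headed for non-IND/IDE agents, so whether that sentence applies here is unclear. The point does not need it, because 10.6231 sets the 30-day rule for deaths without that qualifier.

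Fourth, safety is not a stated goal or endpoint (2.0, 16.1), serious outcomes of cancer progression are not counted as serious adverse events (10.3), and the emulsion's stated half-life is 0.5 to 1 hour (15.15). These points lower the number of related late events to be expected. They do not remove the reporting rules: 10.6231 covers every death to day 30, and attribution can be judged only once an event is known.

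**Conclusion.** The mismatch is real and should be corrected. A site that follows 4.2 and 13.4 to the letter can miss events that 10.4.1, 10.6231 and 10.6232 require and on which the Grade 5 rule in 16.82 depends.

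If the end-of-cycle assessment is kept after the last infusion, the gap is small to moderate: 2 days per patient at the stated maximum cycle length, and 9 or 16 days at the assumed shorter ones, or about 2% to 13% of expected treatment time. For a patient who goes off study at an infusion it can be the whole 30 days.

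The primary endpoint is not affected. Reactions are witnessed by a healthcare provider, and patients without one are censored at their last infusion (11.0, 16.31).

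A reader might also infer biased safety comparisons, because more placebo patients would leave at a reaction if lipids work. A difference in ascertainment between arms is possible, but the documents give no rates from which to show it, and every patient in both arms has the same 30-day window.

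**What to change.** Reconcile 4.2 and 13.4 with Section 10. State that serious adverse events and vital status are ascertained by one phone contact or record review at day 30 after the last study infusion, in both arms and for every off-study reason. Add the matching column to the calendar in 4.1. State also that related serious events and deaths learned of later are still reported, as footnote 1 to 10.4.1 and 10.6232 already require. If the Forms Packet or Data Submission Schedule already provides for this, a cross-reference in 4.2 and 13.4 would do.

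The request should stop at serious events and deaths. Collecting every adverse event to day 30 would go beyond the windows that Section 10 sets.

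The cost is one call or chart check per patient, 40 in all, with no extra visit or test.
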